## 8 CRITERIA FOR EVALUATION AND ENDPOINT

### 8.1 Photographic Assessment

The primary outcome of this study is the overall photographic cosmetic outcome of 9 fraction radiation in NOVEMBER versus published hypofractionation radiation.

Cosmetic effects of radiation can include telangiectasia, breast fibrosis, scar retraction and skin pigmentation changes. As this is not a blinded study, cosmetic assessment will be blinded with digital photography reviewed by a 3 unbiased reviewers. Reviewers will include a radiation oncologist, surgeon and nurse.

Confidential bilateral digital photographs (excluding the face) will be taken with a digital camera:

Photo #1) Bilateral, standing, anterior photo to show both breasts with the arms at 45° from the body and

Photo #2) Unilateral, close up of treated area to show the surgical scar at 24 months post radiation.

Photographs will be captured of both breasts at the following time points:

- Before radiation (Post Lumpectomy and before Radiation)
- 24 months after the completion of radiation

Photographs of both breasts will be collected as above and reviewed by a blinded Central Adjudication Committee according to the modified EORTC Cosmetic Rating System. An on-line training module is available.

### 8.2 Patient Reported Outcomes

We will be using the Breast Q survey tool to assess patient-reported satisfaction with breast, well-being, and overall satisfaction. This tool has been validated for use in patients before and after mastectomy as well as breast conservation, and is provided free of charge for academic research. We will be using the Breast Q Breast Conserving Therapy Module at baseline, 6 months and 24 months after radiation finishes. There are 119 questions with the conceptual framework of the BREAST-Q modules comprised of two overarching themes, which are health-related quality of life (QOL) and patient satisfaction.

Within QOL, there are two scales: Physical, Psychosocial and Sexual Well-being. Within the Psychosocial Well-being scale for patients, there are items that ask about body and a woman's confidence in social settings. Other items cover emotional health and self-esteem. Within the Sexual Well-being scale, there are items that ask about feelings of sexual attractiveness when clothed and unclothed and sexual confidence as it relates to one's breasts, as well as how comfortable or at ease a woman feels during sexual activity. Within the Physical Well-being scales here are questions asking about pain, activity limitations, and sleep problems due to discomfort.

Protocol name: NOVEMBER (Novem- (9), BrEast Radiation), A Phase II trial of a 9 day course of whole breast radiotherapy for early stage breast cancer.

Version Date: 23NOV2021

Principal Investigator: [name]

Within patient satisfaction, there are three other scales: Satisfaction with Breasts, and Satisfaction with Care. "Satisfaction with Breasts," measures body image in terms of a woman's satisfaction with her breasts and asks questions regarding how comfortably bras fit, and how satisfied a woman is with her breast area both clothed and unclothed. Postoperative items ask about breast appearance (e.g., size, symmetry, softness) and clothing issues (e.g., how bras fit; being able to wear fitted clothes). The preoperative modules and the Satisfaction with Care scale will not be included in this study.

Each scale can be used independently and scored separately. The BREAST-Q scoring software, QScore, transforms patient-reported data into summary scores ranging from 0-100 with a higher number meaning better quality of life or higher satisfaction on the various scales.

BREAST Q questionnaires can be collected with pencil/paper or done electronically.

### **8.3 Local and local regional recurrence**

Recurrence data will be collected at 6, 12, 24, and 36 months of follow up and will include a 5 year chart review.

#### **8.3.1 Criteria for Local and regional recurrence**

#### **8.3.2 Local Recurrence**

Local recurrence is defined as histologic evidence of ductal carcinoma in situ or invasive breast cancer in the same quadrant as the lumpectomy of ipsilateral reconstructed breast or breast. A recurrence elsewhere in the breast is considered a local-regional recurrence.

#### **8.3.3 Regional Recurrence**

Regional recurrence is defined as the cytologic or histologic evidence of disease in the ipsilateral internal mammary, ipsilateral supraclavicular, ipsilateral infraclavicular and/or ipsilateral axillary nodes or soft tissue of the ipsilateral axilla. A recurrence in a separate quadrant from the initial lumpectomy will also be scored as a regional recurrence.

#### **8.3.4 Distant Recurrence**

Distant recurrence is defined as the cytologic, histologic and/or radiographic evidence of disease in the skin, subcutaneous tissue, lymph nodes (other than local or regional metastasis), lung, bone marrow, central nervous system or histologic and/or radiographic evidence of skeletal or liver metastasis.

#### **8.3.5 Second Primary Breast Cancer**

Second primary breast cancer is defined histologic evidence of ductal carcinoma in situ or invasive breast cancer in the contralateral breast.

#### **8.3.6 Second Primary Cancer (Non-breast)**

Any non-breast second primary cancer other than squamous or basal cell carcinoma of the skin, melanoma in situ, or carcinoma in situ of the cervix is to be reported and should

Protocol name: NOVEMBER (Novem- (9), BrEast Radiation), A Phase II trial of a 9 day course of whole breast radiotherapy for early stage breast cancer.

Version Date: 23NOV2021

Principal Investigator: [name]

be confirmed histologically whenever possible. If this occurs in the breast radiation field, it will be scored as a radiation induced secondary malignancy.

### 8.3.7 Death

Underlying cause of death is to be reported.

## 8.4 Economic Analysis

A reduction in number of radiation treatments and thereby number of visits to the radiation therapy department will benefit patients directly, both in terms of reduced direct and indirect healthcare costs. Direct healthcare costs are expected to go down because of an expected reduction in health care utilizations services (e.g., office visits, emergency room visits, inpatient admissions). With short-course treatment patients may be able to take less time off from work and/or return to work faster. Potential improvements in cosmetic-outcomes and side effects of radiation therapy with short-course therapy could also translate into a reduction in utilization of health care services, further enhancing the economic impact of hypofractionation. Indirect costs are also expected to be lower for the intervention arm because patients in this arm are expected to resume normal activities sooner. This in turn would help save family caregiver time as well as the cost of dependent care, which will further add to the saving in indirect costs. Therefore, robust measurement of the patient resources used to receive radiation therapy and utilization of health services is a critical component of this trial.

Patients will be given a diary with question domains to be filled out weekly during radiation therapy in order to help improve recall (Appendix II, III and IV).

We will utilize available CPT code charges generated from the time of registration to 2-8 weeks after the completion of radiation therapy. We will utilize the HCI financial data to estimate reimbursable charges.

Questions are adapted from the Medical Expenditure Panel Survey-Household Component (MEPS-HC) created by

AHRQ ([https://meps.ahrq.gov/survey\\_comp/hc\\_survey/2014/DD111214.pdf](https://meps.ahrq.gov/survey_comp/hc_survey/2014/DD111214.pdf)).

For comparison assessment, this survey will be administered to an additional 45 patients undergoing standard of care hypofractionated radiation who are otherwise not eligible or interested in enrollment on this protocol. The Health Care Expense Survey should be provided to the patient and completed by the patient 2-8 weeks post standard of care hypofractionated radiation. The comparison group will either receive a \$20 meal card or be reimbursed for a meal up to \$20, with provision of a receipt from the date of the study visit, after completion of the Health Care Expense Survey. This comparison cohort will be case-matched for distance to treatment facility and employment status.

Collected 2-8 weeks after the completion of radiation:

- Work status prior to breast cancer diagnosis (job for pay or business owner, not including work around the house; including work in a family farm or business even if unpaid).

Protocol name: NOVEMBER (Novem- (9), BrEast Radiation), A Phase II trial of a 9 day course of whole breast radiotherapy for early stage breast cancer.

Version Date: 23NOV2021

Principal Investigator: [name]

- If working number of days working per week.
- If working, number of hours working per day.
- Profession and the job title.
- Total number of hours spent for each radiation treatment (time from leaving home or work to return to home or work).
- Distance from radiation treatment facility from home or work.
- Means of getting to radiation treatment facility (ask if only one modality used or a combination, if a combination record number of days for each modality).

1) Car

- Approximate cost for parking
- Did patient drive, was patient driven, or a combination

2) Shuttle

- Approximate cost

3) Public transportation

- Approximate cost per visit

4) Foot

5) Taxi/car service

- Approximate total cost per visit (both ways)

- Number of radiation treatments during which at least one other person accompanied patient

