## 2.6 Cost Effectiveness

We hypothesize that a 9 fraction course will be more cost effective. Costs will be compared to 45 de-identified patients that were treated with a standard hypofractionated regimen of 19 treatments. Direct costs of medical care to each patient will be estimated using utilization information from HCI financial/claims data. Generalized linear models will then be used to model these costs as a function of treatment, time on study, and all available baseline patient characteristics to assess the extent to which estimated direct cost is impacted by the type of radiation dosing. Given the well-known fact that healthcare costs are typically highly skewed, regression models will employ the appropriate distribution and transformation link.

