#### **4.2 Exclusion Criteria**

##### **Yes/No (Response of “yes” = patient ineligible)**

- 4.2.1  Prior radiation therapy to the chest, neck or axilla.
- 4.2.2  Prior history of ipsilateral breast cancer (invasive disease or DCIS). LCIS and benign breast disease is allowed.
- 4.2.3  History of prior or concurrent contralateral invasive breast cancer. Benign breast disease, LCIS or DCIS of contralateral breast is allowed.
- 4.2.4  Active collagen vascular diseases, such as: systemic lupus erythematosus, scleroderma, or dermatomyositis.
- 4.2.5  Significant post lumpectomy complications requiring an unplanned re-operation or admission for IV antibiotics. Re-operation for margins evaluation or nodal evaluation is acceptable.
- 4.2.6  Co-existing medical conditions with life expectancy < 5 years.
- 4.2.7  Other malignancy within 5 years of registration with the exception of basal cell or squamous cell carcinoma of the skin treated with local resection only or carcinoma in situ of the cervix.
- 4.2.8  Neoadjuvant chemotherapy or adjuvant chemotherapy delivered before radiation.
- 4.2.9  Neuroendocrine carcinoma or sarcoma histology.
- 4.2.10  Concurrent radiation sensitizing medications concurrent with radiation, per treatment physician.

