## 5 TREATMENT PLAN

**Initial surgery** is defined as lumpectomy and any subsequent surgeries related to the initial lumpectomy, including additional margin resection, or lymph node removal.

**Radiation treatment** may begin no later than 84 days after initial surgery.

Chemotherapy must be delivered after (NOT BEFORE) radiation.

**Chemotherapy** is defined as cytotoxic chemotherapy, not biological therapy, such as trastuzumab, pertuzumab, etc.

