### 5.2 Systemic Therapy

Any **adjuvant hormonal therapy** is allowed. It may begin any time relative to the radiation, at the discretion of the treating physician.

**Chemotherapy** is allowed, but must be delivered after radiation therapy. Neoadjuvant chemotherapy is not allowed. Patients may be co-enrolled on systemic therapy trials, if there is no contraindication on the other trial.

Cytotoxic systemic therapy may not be used concurrently with radiation; however, trastuzumab, pertuzumab or other biological therapy may be given concurrently per standard of care.

If cytotoxic chemotherapy is started after radiation, a minimum of 10 days must pass after the last fraction of radiation before beginning chemotherapy. If a patient is experiencing a CTCAE Grade 2 or higher skin reaction, it is recommended that this be extended to 21 days, or until the skin reaction has resolved.

Protocol name: NOVEMBER (Novem- (9), BrEast Radiation), A Phase II trial of a 9 day course of whole breast radiotherapy for early stage breast cancer.

Version Date: 23NOV2021

Principal Investigator: [name]

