## **10 REGISTRATION GUIDELINES**

**Patients must meet all of the eligibility requirements listed in Section 4 prior to registration.**

**Study related screening procedures can only begin once the patient has signed a consent form. Patients must not begin protocol treatment prior to registration.**

Treatment should start within five working days after registration.

To register eligible patients on study, complete a Clinical Trials Office Patient Registration Form and submit to: [[contact]](mailto:[contact]).

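### The section 8.4 charge window can count post-radiation chemotherapy in trial patients and miss pre-radiation chemotherapy in comparators, so the cost comparison can mix chemotherapy timing with number of fractions

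*Combined protocol and SAP*

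**What the plan says.** **Charge window.** Section 8.4: "We will utilize available CPT code charges generated from the time of registration to 2-8 weeks after the completion of radiation therapy". No code restriction follows. Section 9.2.4 counts treatment, drugs, admissions and clinic visits as costs of the intervention. Registration lies close to the start of radiation (section 10): "Treatment should start within five working days after registration".

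**Chemotherapy in trial patients.** It is optional. If given, section 5 fixes the order: "Chemotherapy must be delivered after (NOT BEFORE) radiation". Section 5.2 sets the earliest start: "a minimum of 10 days must pass after the last fraction of radiation before beginning chemotherapy". After a grade 2 or higher skin reaction, "it is recommended that this be extended to 21 days, or until the skin reaction has resolved".

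**Comparators.** Section 8.4 gives the expense survey to 45 patients on standard hypofractionation "who are otherwise not eligible or interested in enrollment on this protocol", matched on distance to the facility and employment status. One ground of ineligibility (4.2.8) is "Neoadjuvant chemotherapy or adjuvant chemotherapy delivered before radiation". Section 2.6 compares direct costs with 45 de-identified patients who had 19 treatments, and models costs "as a function of treatment, time on study, and all available baseline patient characteristics".

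**The concern.** The economic objective (1.2.4) asks what 9 fractions cost compared with a longer standard course. That needs the same kinds of charges to be counted over comparable periods in both groups. Here the window opens shortly before radiation and closes some weeks after it, while the trial's own rules put chemotherapy on the late side of radiation. The comparator pool is open to patients whose chemotherapy was on the early side. The same course of drugs could then be partly booked in one group and omitted in the other.

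The resulting cost difference would reflect drug sequencing and the cut-off date as well as the number of fractions. It would carry through to the incremental cost-effectiveness ratio (ICER) in 9.2.4. With only 45 comparators, a few expensive patients can move a mean.

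**Working it through.** The plan states no figure on this point, so there is none to reproduce. The check is one of dates and eligibility.

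**Inputs**
- Window close: 2 to 8 weeks after radiation, i.e. day 14 to day 56 (8.4).
- Earliest chemotherapy start: day 10 after the last fraction; day 21 as an example of the recommended delay (5.2).
- Window opening in trial patients: registration, about five working days or fewer before radiation (section 10).
- Window opening in comparators: not defined; they are not registered.

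**Step 1. Post-radiation chemotherapy inside the window.** Days counted = max(0, close − start).

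| Window closes | Start day 10 | Start day 21 |
|---|---|---|
| day 14 | 14 − 10 = 4 | 0 |
| day 28 | 28 − 10 = 18 | 28 − 21 = 7 |
| day 42 | 42 − 10 = 32 | 42 − 21 = 21 |
| day 56 | 56 − 10 = 46 | 56 − 21 = 35 |

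Assuming 21-day cycles, the number of cycle starts captured is floor((close − start)/21) + 1 when the start precedes the close. For a day-10 start this is floor(4/21) + 1 = 1 at two weeks and floor(46/21) + 1 = 3 at eight weeks.

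**Step 2. Pre-radiation chemotherapy.** In a comparator treated before radiation, a window opening near the start of radiation captures 0 cycles.

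**Step 3. Illustration of the effect on the mean difference.** Let q be the share receiving chemotherapy, assumed equal in both groups; f the fraction of comparator chemotherapy given before radiation; and k the cycles captured when chemotherapy follows radiation. The excess assigned to the 9-fraction group, in units of one cycle's cost per patient, is q·k − q·(1 − f)·k = q·f·k.

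| q | f | k = 1 | k = 3 |
|---|---|---|---|
| 10% | 0 | 0 | 0 |
| 10% | 0.5 | 0.05 | 0.15 |
| 10% | 1 | 0.10 | 0.30 |
| 30% | 0.5 | 0.15 | 0.45 |
| 30% | 1 | 0.30 | 0.90 |

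The documents give none of q, f, k or the cost of a cycle; these are assumptions that show the range.

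**Step 4. Does anything in the plan remove the difference?** Matching uses distance and employment, neither of which fixes chemotherapy use or order. The model in 2.6 adjusts for baseline characteristics, but post-radiation chemotherapy is not one. Pre-radiation chemotherapy could be treated as one, but it is an exclusion for trial patients, so it is tied to group and there is no overlap on which to adjust. Time on study may absorb part of the variable close, but its start is undefined for comparators. Section 9.2.4 builds the ICER from mean differences and does not say whether they are the adjusted ones.

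**The case against.** The strongest reply is that the plan does not clearly intend to count chemotherapy at all. Section 9.2.4 speaks of direct costs relevant to the treatment or intervention, plus side-effect costs, and 8.4 describes its purpose as measuring what patients use in order to receive radiation. That narrows the likely reading but does not settle it: 9.2.4 also lists drugs, and no sentence sets systemic therapy aside.

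Second, 2.6 and 8.4 may describe different cohorts. Section 8.4 says only that its 45 patients complete the survey, 2.6 calls its 45 de-identified, and 1.2.4 refers to historical controls. This stands: the direct-cost mechanism depends on the two being the same people.

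Third, a reader might infer that trial patients as a rule have chemotherapy in the window and comparators had theirs before. The documents do not support that. Chemotherapy is optional in a node-negative population that includes DCIS alone. Pre-radiation chemotherapy in comparators is possible but not quantified, and patients who were simply not interested could have it after radiation, counted in the same way. If all did (f = 0), the equal-share illustration gives no bias.

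Fourth, the 2-8 week close applies to the assessment in both groups. It makes the captured amount vary between patients but is not in itself a between-group bias.

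**Conclusion.** The gap is real and affects a secondary, exploratory analysis; the primary cosmetic endpoint is untouched. An unrestricted charge window, post-radiation sequencing in the trial and a comparator pool open to pre-radiation chemotherapy together allow drug timing to enter the cost difference. The conclusion assumes one set of 45 comparators and a comparator window like the trial's; a long look-back would change it, but none is described.

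The likely direction for direct costs is against the 9-fraction schedule. It is not certain: chemotherapy shares may differ between groups, and biological therapy, which 5.2 allows during radiation, could offset or add to the effect. The 4 to 46 days are firm for a day-10 start; the money is not derivable.

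A reader might go further and infer that the saving could vanish or reverse. If a share p of trial patients incurred in-window chemotherapy charges equal to C times the true saving, and comparators incurred none, the loss would be p × C of that saving. Choosing p = 20% and C = 5 gives 0.20 × 5 = 100%. Neither value has a source in the documents, zero comparator charges is the worst case, and even this only reaches cancellation.

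Nor do the documents support the inference that indirect costs are inflated in comparators. The survey in Appendix II counts lost work from the first day of radiation to 40 days after it. Comparators might still be off work after earlier chemotherapy, but trial patients starting on day 10 could lose work in the same period. The sign is unknown.

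**What to change.** In sections 2.6, 8.4 and 9.2.4:

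1. Confirm whether the 45 survey comparators and the 45 direct-cost comparators are the same patients.
2. Define one charge window for both groups, opening at a radiotherapy event that both have (planning CT or first fraction) and closing on a fixed day after the last fraction.
3. Exclude systemic-therapy charges from the main direct-cost comparison in both groups. Keep radiation, toxicity, emergency and admission costs, which 8.4 expects to change. Report all charges as a sensitivity analysis.
4. State that the covariate-adjusted cost difference feeds the ICER.

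The cost is revised wording, a code filter on the charge data and a somewhat narrower cost definition; the sensitivity analysis retains the full-charge view. No treatment or visit changes. Recording chemotherapy timing in comparators would help interpretation, but it is new data collection in patients whom 2.6 calls de-identified, and the main comparison above does not depend on it.

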### **5.3 Radiotherapy**

Radiation therapy treatment planning should begin after consultation with the radiation oncologist and prior to radiation treatment.

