#### **Localization, simulation and immobilization**

Simulation and treatment must be performed with the patient in the supine or prone position. Patients should be optimally positioned with alpha cradle casts, vac fix, breast boards, wing boards and/or other methods of immobilization at the discretion of the treating physician.

Methods to minimize the cardiac exposure to RT such as a heart block, gating or breath-hold are allowed at the discretion of the treating physician.

A treatment planning CT scan in the treatment position will be required to define the clinical target volumes (CTV), planning target volumes (PTV), and Organs at Risk (OAR).

Radio-opaque markers are to be placed on the patient's skin in the treatment position as external landmarks at the acquisition of the CT scan to facilitate contouring segmentation of the CT data-set.

The CT scan should extend cephalad to start at or above the mandible and extend sufficiently caudally (or inferiorly) to the inframammary fold to encompass the entire lung volume. A CT scan image thickness of  $< 0.5$  cm should be employed.

External skin localizing marks, which may include permanent tattoos, are recommended for radiation daily localization and set-up accuracy.

Use of IMRT is allowed. Please see the section below for IMRT guidelines.

Calculations shall take into account the effect of tissue heterogeneities.

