#### **The following volumes are to be delineated:**

**Lumpectomy GTV:** Contour using all available clinical and radiographic information including the excision cavity volume, architectural distortion, lumpectomy scar, seroma and/or extent of surgical clips (clips are strongly recommended). Patients without a clearly identifiable lumpectomy bed are not eligible for protocol participation.

Protocol name: NOVEMBER (Novem- (9), BrEast Radiation), A Phase II trial of a 9 day course of whole breast radiotherapy for early stage breast cancer.

Version Date: 23NOV2021

Principal Investigator: [name]

**Lumpectomy CTV:** Lumpectomy GTV + 1 cm 3D expansion. Limit the CTV posteriorly at anterior surface of the pectoralis major and anterolaterally 5 mm from skin and should not cross midline. In general, the pectoralis and/or serratus anterior muscles are excluded from the lumpectomy CTV unless clinically warranted by the patient's pathology. The Lumpectomy CTV should not extend outside of the Breast CTV and should be trimmed if necessary to accomplish this.

**Lumpectomy PTV:** Lumpectomy CTV + 5 mm 3D expansion (excludes heart).

**Lumpectomy PTV Eval:** Since a substantial part of the Lumpectomy PTV often extends outside the patient (especially for superficial cavities), the Lumpectomy PTV is then copied to a Lumpectomy PTV Eval which is edited. This Lumpectomy PTV EvaL is limited to exclude the part outside the ipsilateral breast and the first 5 mm of tissue under the skin (in order to remove most of the build up region for the DVH analysis) and excluding the Lumpectomy PTV expansion beyond the posterior extent of breast tissue (Breast, pectoralis muscles and lung) when pertinent. The lumpectomy PTV should not cross midline. This Lumpectomy PTV Eval is the structure used for DVH constraints and analysis. This Lumpectomy PTV Eval cannot be used for beam aperture generation.

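### The direct-cost window in section 8.4 opens at registration, a date the 45 comparators do not have and which is not tied to consultation or planning in trial patients, so start-up charges can be counted unevenly

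*Combined protocol and SAP*

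**What the plan says.** Section 8.4 (Economic Analysis) defines the charges to be collected: "We will utilize available CPT code charges generated from the time of registration to 2-8 weeks after the completion of radiation therapy". No other start date for direct charges appears in section 2.6, the study calendar (section 7), section 8.4 or section 9.2.4.

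Section 10 governs registration. It states "Patients must meet all of the eligibility requirements listed in Section 4 prior to registration", then "Patients must not begin protocol treatment prior to registration", and "Treatment should start within five working days after registration".

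Planning is timed separately. Section 5.3 says "Radiation therapy treatment planning should begin after consultation with the radiation oncologist and prior to radiation treatment", and section 5.3.1 adds "A treatment planning CT scan in the treatment position will be required". Neither mentions registration.

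The comparison group in section 8.4 is "an additional 45 patients undergoing standard of care hypofractionated radiation who are otherwise not eligible or interested in enrollment". Section 12.1 gives survey volunteers a consent letter and describes no registration step for them. Section 2.6 nevertheless compares direct costs with 45 de-identified patients who had 19 treatments. It takes those costs from HCI financial and claims records and models them on treatment, time on study and baseline characteristics.

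**The concern.** A cost comparison needs the same window in both groups. Here the window opens at an administrative event that exists in only one of them. Even in that group, the event can fall before or after the early, once-per-course work: consultation, planning CT, contouring and plan preparation.

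If those charges are inside the window for one group and outside it for the other, the missing amount goes straight into the estimated saving. Regression on baseline characteristics cannot recover charges that were never extracted. The time-on-study covariate is also undefined for patients who were never on study. At stake are the direct-cost difference in section 2.6 and the numerator of the ICER in section 9.2.4, both under secondary objective 1.2.4.

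**Working it through.** The plan states no expected cost, saving, standard deviation or power for the economic analysis, so there is no figure to reproduce. The check is a comparison of passages followed by an illustrative calculation.

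**Step 1: can the rule be applied to comparators?** Section 10 reserves registration for patients who meet Section 4. The comparators are ineligible or did not want to enrol, so they have no registration date. I read the 45 patients in sections 2.6 and 8.4 as the same group. The rule gives them no start.

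**Step 2: what precedes registration in trial patients?**
- Criterion 4.1.4 concerns the radiation oncologist's plan not to treat regional nodes beyond standard tangents. It must be satisfied before registration, so a radiation oncology decision comes first. The consultation charge will therefore tend to fall before the window opens.
- Section 10 bars protocol treatment before registration but does not name the planning CT or planning. Treatment is meant to follow within about a week.
- Section 5.3.2, in defining the lumpectomy volume, adds "Patients without a clearly identifiable lumpectomy bed are not eligible for protocol participation". This suggests that imaging may come before registration.
- Section 5.3.3 (Ribs) contemplates removing a patient from protocol when the plan cannot achieve coverage. This suggests that planning may come after it.

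The order is therefore not fixed and may differ between trial patients.

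**Step 3: what does uneven capture do?** Let one fraction cost 1 unit. Let F_T and F_C be the start-up charge per trial patient and per comparator, and let t and c be the shares of each group whose start-up charge falls inside the window.

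- True saving = (19 + F_C) − (9 + F_T) = 10 + F_C − F_T
- Apparent saving = 10 + c·F_C − t·F_T
- Error = (1 − t)·F_T − (1 − c)·F_C

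If F_T = F_C = F, the error is F·(c − t). The fraction counts 9 and 19 come from the protocol. F is my assumption, varied from 1 to 10 fraction-equivalents. The table shows the apparent saving, with its share of captured comparator cost in brackets.

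| F | Counted in both | Comparators only | Trial patients only |
|---|---|---|---|
| 1 | 10 (50.0%) | 11 (55.0%) | 9 (47.4%) |
| 3 | 10 (45.5%) | 13 (59.1%) | 7 (36.8%) |
| 5 | 10 (41.7%) | 15 (62.5%) | 5 (26.3%) |
| 10 | 10 (34.5%) | 20 (69.0%) | 0 (0%) |

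Partial capture scales accordingly. With F = 5, all comparators captured (c = 1) and half the trial patients captured (t = 0.5), the error is 5 × (1 − 0.5) = 2.5, so the apparent saving is 12.5.

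With a common start before planning, t = c = 1 and the error is zero, whether or not F_T equals F_C.

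**The case against.** Several points on the other side have force.

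- **A reader might infer from section 5.3.2 that the planning CT must precede registration.** The text does not support that. The lumpectomy volume is drawn from all clinical and radiographic information, including scar and clips, and the condition is not among the Section 4 criteria that gate registration. The Ribs paragraph in 5.3.3 points the other way.
- **A reader might infer that trial patients systematically lose planning charges, so the saving is overstated.** The documents do not establish this. Capture may vary from patient to patient, and if comparators' windows were opened at the first fraction the error could reverse.
- **A reader might treat five working days as a limit.** Section 10 words it as a recommendation.
- **Planning cost may truly differ by regimen.** The trial uses an integrated boost and allows IMRT, and the 19 comparator treatments may include a separate boost. Planning charges need not cancel. This stands, but it is a reason to capture them fully in both groups.
- **The 10-unit benchmark is narrow.** Sections 8.4 and 9.2.4 also count visits, admissions, medications and side-effect treatment. The percentages therefore do not describe error in the planned estimate. The absolute error does not depend on the benchmark.
- **Section 9.2.4 lists the cost of therapy with no registration limit.** Planning might be counted there. This leaves real ambiguity, but 8.4 is the only place that gives a start date for extracting charges, and the two sections are not reconciled.

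One might also say that the analyst would pick a sensible date. None is written, and a date chosen after costs are seen could move the result either way.

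**Conclusion.** The point stands in a limited form. The stated start date cannot be applied to the comparators, and in trial patients it is not tied to the start of radiation care. Consultation charges, and possibly planning charges, can therefore be counted in one group and not the other, which would bias the direct-cost difference and the ICER numerator by the uncaptured amount.

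The sign and size of that bias are unknown. The documents give no prices, no share of patients planned before registration and no start date for comparators. The 1-to-10-fraction range is an assumption, and the figures show only that the error passes one-for-one into the difference.

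The objective affected is secondary, section 9.2.4 describes its cost-effectiveness analysis as exploratory, and it has no stated power or decision threshold. The primary cosmetic endpoint and the safety assessments are untouched. The change is worth making because it is cheap and removes an avoidable bias.

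**What to change.** In section 8.4, replace the registration start with one clinical date that exists in both groups and precedes planning: the radiation oncology consultation or, at the latest, the planning CT. Apply that date when extracting HCI charges for all trial patients and all 45 comparators. In section 9.2.4, state that the cost of therapy uses the same window. In section 2.6, the time-on-study covariate should run from the same date, so that it is defined for comparators.

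The cost is a sentence or two of text and a changed start date in the billing extraction. The plan already relies on HCI financial data for both groups, so charges billed there should need no new collection from patients. The date should be fixed before costs are compared.
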